6.3. Sample size

This study aims to collect data for one year. In accordance to the data reported in 2022, we will collect 100 dengue infection cases from each public health center and 200 cases from the Tangerang District Hospital.

It is expected that the Tangerang District Hospital, Kelapa Dua Public Health Center and Bojong Nangka Public Health Center can represent the population in Tangerang District.

VII. REFERENCES

3. da Costa VG, Marques-Silva AC, Moreli ML. *A meta-analysis of the diagnostic accuracy of two commercial NS1 antigen ELISA tests for early dengue virus detection*. *PLoS One*. 2014 Apr 11;9(4):e94655. doi: 10.1371/journal.pone.0094655. PMID: 24728377; PMCID: PMC3984211.

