Considering the consequences of undiagnosed dengue infection, the inability to detect DENV-4 using NS1 rapid test may lead to misclassification of cases as non-dengue, resulting in different therapy/ management. This may adversely affect patient therapy, leading to delayed or inappropriate management potentially leading to prolonged illness or worsening of symptoms.

Overcoming the limitations of current diagnostic methods is critical to ensure quick and precise treatment for individuals infected with DENV-4. This is particularly relevant in the context of vaccine development and clinical trials, where accurate serotype identification is essential to evaluate vaccine efficacy and effectiveness. Improving diagnostic capabilities and awareness of the presence and potential impact of DENV-4 infection will contribute to more effective management and control strategies for dengue, ultimately reducing the burden of disease in affected populations. By addressing these issues, healthcare providers and researchers can improve patient prognosis and reduce the challenges posed by DENV-4 infection.

Tangerang, located in Banten province, Indonesia, has a high risk of dengue virus transmission due to its dense population and favorable environmental conditions for mosquito breeding. Despite vector control efforts, dengue remains a significant health challenge in the region. In 2022, as many as 50-100 dengue cases were reported in each public health center and more than 200 patients were hospitalized due to dengue infection.

Focused study in Tangerang, which includes hospitals and public health centers, is essential to obtain local data that can be used as a source of information for interventions that will improve a broader understanding of dengue epidemiology in Indonesia. Tangerang District Hospital is a referral hospital for all public health centers that has several national and multinational clinical studies. Including intervention studies, Tangerang District Hospital has a well-equipped infectious disease laboratory to conduct molecular and serological tests. Collaborating with INA-RESPOND lab, we are also able to conduct Plaque Reduction Neutralization Test (PRNT).

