2.2. Secondary objectives

- To assess the prevalence of dengue virus infection among patients with acute fever
- To assess the prevalence of infection with DENV-4 and other serotypes as well as clinical characteristics, immunologic and virologic profiles important for vaccine trials and implementation
- To assess human and viral factors associated with severity of febrile illness due to dengue virus infection
- To increase the capacity of Tangerang District Hospital's Infectious Disease Laboratory/ INA RESPOND Reference Laboratory to perform plaque reduction neutralization test (PRNT).
- To identify other etiologies of fever in Tagerang district

III. CLINICAL HYPOTESIS

Dengue fever is a hyperendemic disease in Tangerang district, Indonesia.

DENV-4 infection is more frequently found at the primary health centers than at the hospital because the clinical symptoms are milder.

Several human and viral factors, such as age, nutrition status, immune status, serotypes, types of infections (primary/secondary) are associated with severity of symptoms.

IV. ETHICAL APPROVAL

This study will be conducted in accordance with ethical guidelines and obtained permission from the relevant institutions and the ethics committee of Tangerang District Hospital.

V. METHOD

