5.1. Study design

This study is a prospective observational study that will be conducted in Tangerang Regency, Indonesia. In this study, data will be collected from patients who seek treatment at the Tangerang District Hospital, Kelapa Dua Public Health Center and Bojong Nangka Public Health Center in a one-year period from January 2024 to December 2024. Both public health centers have densely populated areas and have experience in conducting clinical research on COVID-19 vaccination.

Patients suspected of dengue infection will be screened using inclusion and exclusion criteria. Selected participants will be seen at the first visit as clinical data will be collected, routine hematology test and NS-1 RDT will be conducted. Blood specimens will be collected for further testing at Tangerang District Hospital's Infectious Disease Laboratory.

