6.1. Variable

Variables collected include age, gender, demographic characteristics, clinical symptoms, medical history, and history of previous dengue infection. The prevalence, immunologic and virologic characteristics, clinical features, and severity of DENV1-4 infection will also be recorded.

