6.2. Statistical analysis

Statistical analysis will include descriptive statistics to summarize the demographic and clinical characteristics of participants. Prevalence estimates of DENV1-4 will be calculated with their respective confidence intervals. Prevalence, demographic and clinical comparisons between DENV-4 and other serotypes will be made using appropriate statistical tests, such as chi-square or Fisher's exact test.

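### Three unsampled facilities with fixed case quotas are expected to represent Tangerang District; pooled serotype shares reflect the quota mix, and a health-center versus hospital difference in DENV-4 can reflect place as well as care level

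*Combined protocol and SAP*

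**What the plan says.** Section 6.3 sets the targets from 2022 counts: "we will collect 100 dengue infection cases from each public health center and 200 cases from the Tangerang District Hospital". It then expects that the three facilities "can represent the population in Tangerang District". It describes no sampling frame, random choice of sites or weighting. Section 5.3 extends recruitment until the specified number is reached, so the site mix is fixed by design.

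Section 5.1 describes the centers: "Both public health centers have densely populated areas and have experience in conducting clinical research on COVID-19 vaccination". The background says that "Tangerang District Hospital is a referral hospital for all public health centers". Section 5.4 recruits patients who seek care at any of the three facilities with dengue-like symptoms and does not restrict by residence.

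Section III contains the hypothesis that "DENV-4 infection is more frequently found at the primary health centers than at the hospital because the clinical symptoms are milder".

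In section 6.2, "comparisons between DENV-4 and other serotypes will be made using appropriate statistical tests, such as chi-square or Fisher's exact test". It names no contrast between settings and no stratification by site or residence. Section 6.1 lists the data items: "Variables collected include age, gender, demographic characteristics, clinical symptoms, medical history, and history of previous dengue infection". Neither residence nor referring center is named.

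**The concern.** Two inferences are at stake.

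The first is descriptive. The primary objective (2.1) is set at district level, and 6.2 promises prevalence estimates for DENV-1 to DENV-4 with confidence intervals. With fixed quotas, a single pooled figure weights the sites by the quotas and not by how dengue is distributed in the district. A confidence interval around it does not cover that error.

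The second is causal. Section III attributes an excess of DENV-4 at health centers to milder illness. Health-center cases come through two centers, while hospital cases may come from any center's area. If the serotype mix varies within the district, the two settings can differ in DENV-4 share even when care level has no effect. The opposite pattern could hide or reverse a real effect. Nothing in the plan as written would let a reader tell these cases apart.

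**Working it through.** **The plan's own figures.** No error rate, power, effect size or precision target is stated, so there is no sample size formula to reproduce. The targets can only be set against the 2022 counts in the background: "as many as 50-100 dengue cases were reported in each public health center and more than 200 patients were hospitalized". The target of 100 per center is the top of the 50-100 range, and 200 is the lower bound of the hospital count. The total is 100 + 100 + 200 = 400.

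**Pooled share.** With these quotas, pooled share = (100·p1 + 100·p2 + 200·pH)/400 = 0.25·p1 + 0.25·p2 + 0.50·pH, where p1 and p2 are the DENV-4 shares at the two centers and pH is the share at the hospital. The weights 0.25, 0.25 and 0.50 come from the quotas. They would match the district only by coincidence.

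**Setting contrast.** Inputs from the documents: 2 × 100 = 200 health-center cases and 200 hospital cases. The rest is assumed, because the documents give no figures:
- p_in, the DENV-4 share inside the two center areas, and p_out, the share elsewhere;
- w, the proportion of hospital cases living in the two areas;
- no effect of care level, all health-center cases living inside the two areas, and every case serotyped.

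Then hospital share = w·p_in + (1 − w)·p_out, and false gap = p_in − hospital share = (1 − w)·(p_in − p_out). For p_in = 15%, p_out = 5% and w = 0.1, the hospital share is 1.5% + 4.5% = 6% and the gap is 9 points.

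The last column is the probability that a two-sided Fisher's exact test at 5% is significant, by full enumeration of both binomials, 200 versus 200.

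| p_in | p_out | w | Hospital share | Gap (points) | Falsely significant |
|---|---|---|---|---|---|
| 15% | 5% | 0.1 | 6% | 9 | 0.809 |
| 15% | 5% | 0.2 | 7% | 8 | 0.682 |
| 15% | 5% | 0.4 | 9% | 6 | 0.399 |
| 15% | 5% | 0.7 | 12% | 3 | 0.111 |
| 10% | 5% | 0.1 | 5.5% | 4.5 | 0.324 |
| 10% | 5% | 0.2 | 6% | 4 | 0.252 |
| 10% | 5% | 0.4 | 7% | 3 | 0.144 |
| 10% | 5% | 0.7 | 8.5% | 1.5 | 0.057 |
| 5% | 15% | 0.1 | 14% | −9 | 0.846 |
| 5% | 15% | 0.2 | 13% | −8 | 0.765 |
| 5% | 15% | 0.4 | 11% | −6 | 0.537 |

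When all hospital cases are local (w = 1) the gap is 0. The rejection rate is then 0.036 (15% in both settings) or 0.034 (10%), below 5% because Fisher's test is conservative.

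The last three rows reverse the gradient: the false difference then runs against the section III hypothesis. A milder gradient matters little: 7% inside and 5% elsewhere, with w = 0.1 to 0.4, gives 0.080 to 0.051.

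**Precision of a comparison limited to residents of the two areas.** If 10%, 20% or 40% of 200 hospital cases are local, 20, 40 or 80 remain. Against 200 health-center cases, a true difference of 15% versus 5% would be detected by Fisher's test with power 0.10, 0.32 and 0.66.

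**The case against.** Several points on the other side stand.

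- A reader might infer that the centers were picked for their density. Section 5.1 gives density as an attribute alongside research experience and states no selection rule. The background calls Tangerang as a whole densely populated, so density alone does not set the two areas apart.
- A referral role does not say where hospital patients live, and people living nearby may attend directly. No catchment map or local proportion is given. The documents establish that residence is unrestricted, not how far the catchments differ.
- Section 6.2 contains no health-center versus hospital test, and the setting statement is a section III hypothesis, not an objective. The confounding affects how that hypothesis is interpreted, not a written analysis.
- The representativeness sentence is phrased as an expectation and feeds no calculation, and 6.2 does not expressly promise one pooled district estimate. Residence may fall under the demographic items; the case report form is not in the documents.
- Stratifying by residence would add little. Few health-center patients are likely to live outside the two areas, so the analysis largely reduces to the restricted comparison, whose power is low.

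These points limit the size claimed and the remedy. They do not supply a sampling basis for the 6.3 sentence or a way to separate care level from place.

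**Conclusion.** The concern holds in a limited form. The district-level expectation in 6.3 has no support in the design, a pooled serotype share would reflect the 100/100/200 quotas, and a difference in DENV-4 between settings could not be put down to milder symptoms alone.

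The size is unknown. Under the positive gradients assumed (15% or 10% inside, 5% elsewhere, 10-70% of hospital cases local), the false-positive rate runs from about 6% to 81%. The lower end is close to nominal. It is tempting to conclude that the hypothesis will probably be confirmed falsely, or that the top of this range is what to expect. The documents support neither reading: they give no DENV-4 share by area and no local proportion, and the bias could equally run the other way. Nor do they show that the serotype mix actually varies within the district, only that the plan could not detect or allow for it.

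This should be corrected. It is a matter of scope and interpretation, not an arithmetic error.

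**What to change.** 1. In 6.3, replace the representativeness sentence with: *results apply to patients aged 4 years or over attending these three facilities*.
2. In 6.1 and the case report form, name sub-district of residence among the demographic items.
3. In 6.2, report DENV-4 shares by site with confidence intervals, not as one pooled district figure.
4. In 6.2, state that if the settings are compared, the comparison will also be shown limited to residents of the two center areas, as an estimate with its confidence interval. State too that a setting difference will not be attributed to milder symptoms from the unrestricted comparison alone.

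The cost is one data field, easiest to capture at enrolment, and a few sentences. No sites, participants or procedures are added. The downside is a narrower claim and low precision in the restricted comparison, with 20-80 hospital cases if 10-40% are local. It should therefore be read as an estimate, and a non-significant result should not be taken as evidence of no difference.
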